3.2.2 Specific Aims

SA1: Determine the efficiency and effectiveness on PD signs of aDBS, triggered by patient-specific resting or movement state neural activity, compared to cDBS, using the UPDRS III and validated high-resolution kinematic metrics of tremor, bradykinesia and freezing of gait (FOG).

Primary Hypothesis: Resting state aDBS will reduce energy consumption compared to cDBS as well as improve overall motor outcome, but may have differing effects on the individual PD motor signs.

SA1a. Determine the neural classifier of the resting or movement state to use as a trigger for aDBS. Hypothesis: Patient-specific beta band synchrony is a classifier of the off therapy resting or movement state in PD and can be used as a trigger for aDBS^{1,2}. Using individualized algorithms, resting or movement state neural activity will be tested as the stimulation trigger, activating aDBS when beta power is above a specific threshold. SA1b. Compare the efficiency and effectiveness on PD symptoms of aDBS (using the patient specific resting state neural classifier) compared to cDBS at the same neurostimulation parameters.

SA2: Determine whether aDBS using a kinematic classifier pertinent to the patientspecific phenotype is more efficient and/or effective on PD symptoms than aDBS using the using the patient’s specific resting or movement state neural classifier and/or cDBS.

Secondary Hypothesis: Different PD motor phenotypes may respond better to aDBS triggered by the kinematic classifier respective to that state than to aDBS triggered by the resting or movement state neural classifier or to cDBS.

SA2a. Determine the kinematic classifiers for the states of tremor and bradykinesia, and develop the control policy algorithms of optimal DBS settings that improve each motor abnormality. SA2b. Compare the efficiency and effectiveness on PD symptoms of tremor or bradykinesia kinematic aDBS versus resting or movement state neural aDBS and cDBS.

SA3: Determine whether aDBS is more efficient and effective than cDBS in the optimized on medication state after six months of cDBS.

Tertiary Hypothesis: Neural and/or kinematic classifiers and control policy algorithms will need to be adapted to different medication states, making aDBS more or less useful. After six months of cDBS plus medication, SA1 and SA2 will be repeated in the optimized on medication state. The control policy algorithms will be adjusted as necessary to adapt to this state.

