3.2.6 Recruitment

Subjects with Parkinson's disease who have been accepted for DBS implantation will be asked if they wish to participate in this study. All subjects will have undergone challenged on medication and practically defined off medication evaluations by a fellowship-trained movement disorders neurologist and detailed neuropsychological testing by a neuropsychologist prior to being presented at the movement disorders surgical review board. The movement disorders surgical review board consists of the neurosurgeons, movement disorders neurologists, psychiatrist, neuropsychologist, and nurse specialists, who evaluate each candidate's suitability for surgery and reach a consensus decision about each person. If s/he is accepted for DBS, s/he is scheduled to meet the neurosurgeon. At this visit they will be met in person by the research coordinator, who will with permission sit down in person with them and any family present to explain the study and review the informed consent. Feasibility of and time for recruitment: on average the Stanford Movement Disorders Surgical Review board accepts 6 – 10 patients for DBS per month. If it is assumed conservatively that 50% of patients asked will consent, then the recruitment of 15 subjects will take a maximum of five months. We recruit subjects currently for intra-operative investigations, which we think would be harder to recruit for than the current study and our acceptance rate is higher than 80%.

We will also recruit subjects who are participating in or have completed Study 1 to consent to and complete Study 2. In order to account for study attrition additional subjects (up to 10 additional) will be recruited into study 2.

Sample Size/Power Analysis: Our preliminary data: change ON versus OFF DBS (mean +/- std dev): beta band power = 57 +/- 6², UPDRS = 58 +/- 22%⁵, Vrms 45% +/- 63%³. Power analysis (paired t-test, p=0.8, alpha =0.001, to allow for multiple comparisons) on the above data gave the largest sample size required for significant outcomes = 27 (STNs), which is similar to the sample size (21) needed to detect difference between aDBS and cDBS reported in previously published results¹.

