3.2.10 Data Analysis

Experimental outcomes: Beta power, UPDRS III and quantitative measures of tremor (rest tremor recording for 1 minute), bradykinesia (WFE task) and FOG (using a Stepping in Place (SIP) task and gait analysis), and time DBS ON over the 30 minutes on aDBS.

Number of arms: (One) Patients will be used as their own controls.

All quantitative data will be post-processed using custom MATLAB software (The MathWorks, USA).

1. **Repetitive wrist flexion-extension movement – rwFE:** The Motus motion analysis system will be used to obtain an objective quantitative assessment of bradykinesia by measuring hand angular velocity during a quantitative repetitive wrist flexion-extension task (rwFE). The system consists of sensors in which vibrating quartz crystals act like solid-state gyroscopes and produce an analog signal whose voltage is proportional to the angular velocity when rotated about its measurement axis. These sensors are unlike conventional accelerometers in that they are indifferent to their orientation with respect to gravity. Each sensor weighs about 60 g, has a maximum range of 1,900 degrees per second, a low noise level of 1 degree per second RMS, and a flat response to 30 Hz. The angular velocity data will be digitized at a rate of 100 samples per second per sensor. The root mean square velocity of angular movement (Vrms) will be used as an indication of the average speed at which the flexion-extension task is performed. The frequency spectrum of the angular velocity will be analyzed using a fast Fourier transform (FFT) analysis in each trial to ensure that patients' movements are not dominated by a fast-action tremor (7–12 Hz).
2. **Tremorography;** Using the above mentioned angular velocity sensors, the angular velocity data during rest and/or postural poses will be digitized at a rate of 100 samples per second per sensor and the frequency spectrum will be will be analyzed using an FFT analysis to detect and quantify the type of tremor (rest 4-6 Hz or action/postural 712 Hz) that is present.

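### The plan states a primary hypothesis but no primary outcome, analysis test or order of testing; its only error-rate rule is a flat alpha of 0.001 in the sample-size sentence

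*Combined protocol and SAP*

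**What the plan says.** - **Hypothesis.** Section 3.2.2 states: "Primary Hypothesis: Resting state aDBS will reduce energy consumption compared to cDBS as well as improve overall motor outcome". It therefore has two parts, energy and motor outcome. SA1 assesses PD signs by the UPDRS III and kinematic measures.
- **Outcomes.** Section 3.2.5 lists beta power, UPDRS III, tremor, bradykinesia, speech, freezing of gait and time with DBS on. Section 3.2.10 gives nearly the same list, without speech: "Experimental outcomes: Beta power, UPDRS III and quantitative measures of tremor" and so on. Neither marks one outcome as primary.
- **Analysis.** Section 3.2.10 says that patients are their own controls and describes signal processing for each task. It names no hypothesis test, significance level, order of testing or multiplicity rule.
- **Error rate.** The one statement is in the sample-size paragraph of 3.2.6, for a paired t-test with a stated p of 0.8: "alpha =0.001, to allow for multiple comparisons". The comparisons being allowed for are neither listed nor counted.
- **Basis of the sizing.** The effects are "change ON versus OFF DBS (mean +/- std dev"), and the calculation "gave the largest sample size required for significant outcomes = 27 (STNs"). For the contrast in the primary hypothesis, the plan cites only a "sample size (21) needed to detect difference between aDBS and cDBS reported in previously published results", with no effect, SD, alpha or power.

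**The concern.** A strict flat alpha gives the question the study was designed to answer no more protection than any side measure. A single test placed first in a fixed order can be run at 0.05 without raising the familywise error. At 0.001 the same test gives up power, and how much depends on the size of the effect.

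The opposite reading also has a cost. If 0.001 was meant only for sizing, the analysis has no stated level and no lead outcome, so any outcome, contrast or medication state could be presented afterwards as the main result. Beta power is the outcome most exposed to this. It is the trigger for neural aDBS in SA1a, it heads both outcome lists, and it is one of the three sizing inputs. A controller that acts on beta power can change beta power without any motor benefit.

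**Working it through.** **Step 1. Reproduce the plan's figure.** The inputs are from 3.2.6, with d = mean / SD:

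- beta power: 57 / 6 = 9.5
- UPDRS: 58 / 22 = 2.64
- Vrms: 45 / 63 = 0.714, the smallest effect, which therefore sets the sample size

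I read the stated p of 0.8 as 80% power. Sidedness is not given. For a paired t-test, n is the smallest value at which a noncentral t with n − 1 degrees of freedom and noncentrality d√n exceeds the critical value with probability 0.80. For Vrms:

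| Alpha | Two-sided t | One-sided t |
|---|---|---|
| 0.001 | 39 | 36 |
| 0.005 | 31 | 27 |
| 0.01 | 27 | 23 |
| 0.05 | 18 | 14 |

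The normal approximation, ((z_alpha + z_power) / d)², gives 34 (two-sided) or 31 (one-sided) at 0.001. So 27 does not reproduce at 0.001 by any of these routes. It matches two-sided 0.01 exactly (the same calculation as one-sided 0.005); the normal approximation at two-sided 0.005 also gives 27. At n = 27, Vrms has 51.5% power at two-sided 0.001 and 81.5% at two-sided 0.01. Either the alpha or the 27 appears to be misstated.

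**Step 2. Cost of 0.001 for the primary contrast.** The sizing effects compare DBS ON with OFF, so they say nothing direct about aDBS against cDBS. The effects below are assumptions. They are in SD units of the within-patient difference, with n = 30 patients (the enrolment ceiling in 3.2.3) and a two-sided paired t-test. Power = P(T > t_crit), where T is noncentral t with 29 degrees of freedom and noncentrality d√30; t_crit is 3.659 at 0.001 and 2.045 at 0.05.

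| Assumed effect (SD) | Power at 0.001 | Power at 0.05 |
|---|---|---|
| 0.4 | 10% | 56% |
| 0.5 | 21% | 75% |
| 0.6 | 38% | 89% |
| 0.7 | 57% | 96% |
| 0.8 | 75% | 99% |
| 1.04 | 97% | about 100% |

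The effect detectable with 80% power is 0.83 SD at 0.001 and 0.53 SD at 0.05.

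**Step 3. What the cited 21 could imply.** At 80% power, n = 21 corresponds to d = 0.64 if it was computed at two-sided 0.05, or d = 1.04 if computed at 0.001. With 30 patients, power at 0.001 versus 0.05 is then 46% versus about 92%, or 97% versus about 100%. The documents do not say which applies.

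**Step 4. If alpha was really 0.01.** At 0.5 SD and n = 30, power is 50%, against 75% at 0.05. The penalty is smaller but still material.

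**The case against.** **The level may not be an analysis level.** The value 0.001 appears once, in a sample-size sentence. A reader might infer that every outcome will be tested at one fiftieth of the usual level. The documents do not say so, because 3.2.10 sets no level at all. This stands, and it is why the point is conditional.

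**The power loss may be small.** A reader might infer that the primary hypothesis loses most of its power. That holds only for modest effects: at n = 30 and 0.6 SD, power is 38% rather than 89%, but at 0.7 SD more than half of it remains. For large effects the loss is negligible. The plan's own UPDRS input gives about 100% power at either level, though for ON versus OFF DBS, which is not the contrast in the hypothesis. Power for the primary hypothesis cannot be computed from these documents. This stands.

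**The strict alpha does control false positives.** One could count 7 outcomes × 3 contrasts × 2 medication states = 42 tests and quote 1 − 0.95^42 = 88%. That figure requires reading all 42 at 0.05, which the plan does not propose; at 0.001 it is 1 − 0.999^42 = 4.1%. The count is also a construction. Tremor is measured only where visible, kinematic aDBS depends on phenotype, and the outcomes are correlated. The 88% should not be used.

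**The primary hypothesis is itself two claims.** It is not true that it needs no adjustment: the energy and motor parts must be ordered, or both required to succeed. This stands and shapes the fix.

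**This is an open-label pilot, and the lead outcome can be guessed.** Sections 3.1 and 3.2.2 point to the UPDRS III. That is fair, but guessing is not designation, and a study with a stated primary hypothesis that is powered for significance should name its test.

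**Conclusion.** The point holds as a gap in specification. There is a primary hypothesis but no primary outcome, no analysis test, no analysis alpha and no order of testing; the only rule is a flat 0.001 attached to the sample size.

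If 0.001 is carried into the analysis, the cost to the primary comparison at n = 30 runs from large (21% versus 75% at 0.5 SD) to negligible (97% versus about 100% at 1.04 SD). If it is not carried over, selection among outcomes is unconstrained. These figures assume a two-sided paired t-test, one within-patient difference per patient, all 30 patients contributing, and effect sizes that the documents do not supply. The plan's 27 is counted in STNs, whereas UPDRS III would normally be compared per patient, so the two counts are not interchangeable.

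The mismatch in the sizing sentence does not depend on an assumed effect: 80% power for Vrms at 0.001 needs 31 to 39 depending on method and sidedness, not 27.

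This is a cheap improvement, not a fatal flaw.

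**What to change.** Add a paragraph to 3.2.10 that does the following:

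1. **Primary test.** Blinded UPDRS III, resting-state neural aDBS minus cDBS, off medication at the first follow-up visit (the SA1b session), paired, two-sided alpha 0.05. Section 3.2.7 already provides blinded rating and two further independent video raters; say which rating, or what combination, is analysed.
2. **Second in fixed order.** The energy part of the primary hypothesis, as time with DBS on, tested at 0.05 only if the first test succeeds.
3. **Everything else.** The other outcomes, the kinematic aDBS contrasts and the six-month on-medication comparisons become secondary with Holm correction, or are labelled exploratory.
4. **Beta power under neural aDBS.** Report it as a check of the controller, not as evidence of effectiveness.

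In 3.2.6, state the sidedness and reconcile alpha with the sample size: 0.001 with 39 (two-sided t), or 27 with the alpha that was actually used. Say whether that alpha applies to the analysis. Redo the sizing for aDBS against cDBS per patient, with the assumed effect stated.

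The cost is some text and a short recalculation. The new order of testing uses data already planned, with no added visits or measurements. The downside is that the other outcomes lose equal standing and become secondary or exploratory.

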2. REPORT OF PRIOR INVESTIGATIONS

For prior investigations with Medtronic DMF 2010 – Activa PC+S Neurostimulation System, please refer to Medtronic Right of Reference Letter located in **Appendix B** and [REDACTED] Master File # [REDACTED] (PDF Page 58).

Clinical investigations of the standard DBS system

The [name] Lab has performed several clinical investigations using the FDA approved Medtronic device, the Activa PC Deep Brain Stimulation (DBS) system, since 2005. From here on, this term - the DBS system - will refer to the standard (nonsensing) implantable pulse generator (IPG), its connectors, leads and the four electrodes that are implanted in the brain. We were the first to show that the presumed brain biomarker of Parkinson's disease (PD), specifically the beta rhythm, was attenuated after short periods of DBS¹. We subsequently showed that the resting beta rhythm was stationary and was similar across hemispheres in individuals but different among people with PD, and that there was evidence that this abnormal rhythm in the brain in PD was a property of a widespread bilateral sensorimotor network^{2,3}. We demonstrated that there was a gradient in the power of this rhythm within the main target nucleus for DBS in PD, the subthalamic nucleus (STN), and that DBS both at this site and dorsal to the nucleus attenuated the beta rhythm power in a voltage-dependent fashion in PD and showed prolonged attenuation of beta power after longer periods of DBS^{2,4,5}. We have also reported that such abnormal electrophysiology is seen in both primary and secondary dystonia in the brain and that DBS also attenuates beta rhythm power in dystonia in the target nucleus, the globus pallidus interna (GPI). We are in the pilot stages of our investigations of abnormal electrophysiology during tremor and movement and the effects of DBS on such. With the technological development of the sensing IPG, we will be able to move these experiments from the operating room to the laboratory.

3. INVESTIGATIONAL PLAN (Study 2: Adaptive Closed Loop

Neuromodulation for Parkinson's Disease)

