3.2.3 Study Design, Setting/Location

This is an open-label pilot study of up to 30 people with Parkinson's disease. All experiments will be performed in the Stanford Human Motor Control and Balance Laboratory in the department of Neurology and Neurological Sciences at Stanford University Medical Center. A unique aspect of the Stanford Movement Disorders Center is the Stanford Human Motor Control and Balance Laboratory, in which we have developed several quantitative measures of motor control and a parallel line of research in human motor control in movement disorders. These measures have been validated with the clinical scale most widely used in PD research, the UPDRS III, as stated above.

Study Population

The study will be carried out in up to 30 people with moderate to advanced PD who will have been evaluated and approved to have subthalamic deep brain stimulation to treat their motor signs. Subjects who have been implanted with Activa PC+S and are participating or have completed Study 1 will be asked to complete Study 2. In order to account for study attrition additional subjects (up to 30) will be recruited into study 2.

Battery life on the Activa PC + S (research device) and the Activa PC (FDA-approved clinical device) is estimated to last approximately 3-5 years. A limited number of subjects will be invited to be replaced with an Activa PC+S, should they chose to remain in the study. Invitations to receive a replacement Activa PC+S will depend on the focus of future experiments, quality of signal, and device availability. If the patient would prefer not to continue in the study, or if they are not invited to continue, they may proceed with the standard implantation of the non-research device.

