3.2.4 Eligibility Criteria

The eligibility criteria are the same as those used for Study 1

Inclusion criteria:

1. A diagnosis of idiopathic Parkinson's disease with bilateral symptoms at Hoehn and Yahr Stage \geq II.
2. Documented improvement in motor signs on versus off dopaminergic medication, with a change in the Unified Parkinson's Disease Rating Scale motor (UPDRS III) score of \geq 30% off to on medication.
3. The presence of complications of medication such as wearing off signs, fluctuating responses and/or dyskinesias, and/or medication refractory tremor, and/or impairment in the quality of life on or off medication due to these factors.
4. Subjects should be on stable doses of medications, which should remain unchanged until the DBS system is activated. After the DBS system is optimized (during which time the overall medication dose may be reduced to avoid discomfort and complications such as dyskinesias), the medication dose should remain unchanged, if possible, for the duration of the study.
5. Treatment with carbidopa/levodopa and with a dopamine agonist at the maximal tolerated doses as determined by a movement disorders neurologist.
6. Ability and willingness to return for study visits at the initial programming and after three, six, and twelve months of DBS.
7. Age > 18

Exclusion criteria:

1. Subjects with significant cognitive impairment and/or dementia as determined by a standardized neuropsychological battery.
2. Subjects with clinically active depression, defined according to the Diagnostic and Statistical manual of Mental Disorders, Fourth Edition (DSM-IV) criteria and as scored on a validated depression assessment scale.
3. Subjects with very advanced Parkinson's disease (Hoehn and Yahr stage 5 on medication (non-ambulatory)).
4. Age > 80 .
5. Subjects with an implanted electronic device such as a neurostimulator, cardiac pacemaker/defibrillator, or medication pump.
6. Subjects who are pregnant, are capable of becoming pregnant, or who are breast feeding.
7. Subjects with an MRI showing focal brain lesions that could indicate a non-idiopathic movement disorder.
8. Subjects having a major comorbidity increasing the risk of surgery (prior stroke, severe hypertension, severe diabetes, or need for chronic anticoagulation other than aspirin).
9. Subjects having any prior intracranial surgery.
10. Subjects with a history of seizures.
11. Subjects who are immunocompromised.
12. Subjects with an active infection.

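### The sample size is counted in subthalamic nuclei with no allowance for two sides in one person, no analysis unit is named, and the figure of 27 does not follow from its own inputs

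*Combined protocol and SAP*

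**What the plan says.** Section 3.2.6 gives the only hypothesis test in the documents: "paired t-test, p=0.8, alpha =0.001, to allow for multiple comparisons" (p=0.8 is read here as power). The inputs are given as "change ON versus OFF DBS (mean +/- std dev"): beta power 57 ± 6, UPDRS 58 ± 22% and wrist-movement velocity (Vrms) 45% ± 63%. The calculation "gave the largest sample size required for significant outcomes = 27 (STNs"). The same section estimates that "the recruitment of 15 subjects will take a maximum of five months", and section 3.2.3 describes an "open-label pilot study of up to 30 people".

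Section 3.2.10 says "Patients will be used as their own controls" but names no test, model or unit of analysis. Section 3.2.7 randomises the order of conditions for each subject. Section 2 reports that the resting beta rhythm is "similar across hemispheres in individuals but different among people with PD". Section 3.2.4 requires "idiopathic Parkinson's disease with bilateral symptoms at Hoehn and Yahr Stage" II or above. No section mentions a within-person correlation, a design effect, averaging of sides, or a rule of one side per person.

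**The concern.** A paired t-test removes the level that each nucleus shares between conditions. It does not remove any correlation between the left and right treatment differences of the same person. If that correlation is positive, 27 nuclei carry less information than 27 independent units, the standard error is too small, and the alpha of 0.001, chosen to cover multiple comparisons, is exceeded.

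A positive correlation is plausible. The group's own work points to similar sides within a person for resting beta. Condition order is set per subject, so any order, fatigue or washout effect falls on both sides together.

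Stepping and gait are whole-person tasks, speech is one recording per person, and UPDRS III is listed without per-side scoring. A size in nuclei has no clear meaning for these outcomes, yet UPDRS is among the inputs.

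**Working it through.** **1. The plan's own figure.** Standardised effects are mean/SD: beta power 57/6 = 9.5; UPDRS 58/22 = 2.64; Vrms 45/63 = 0.714. Paired t-test, 80% power, two-sided alpha 0.001 (noncentral t):

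| Outcome | Units needed |
|---|---|
| Beta power | 4 |
| UPDRS | 8 |
| Vrms | 39 |

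Vrms drives the size. The plan does not state sidedness. One-sided, Vrms needs 36; the normal approximation gives 34 (two-sided) or 31 (one-sided). None of these is 27. The t-test at two-sided alpha 0.01 gives 26.3, rounded up to 27, so the stated figure matches 0.01 rather than 0.001. With 27 independent units at alpha 0.001, power is about 52% two-sided or 61% one-sided.

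**2. Are both sides counted?** 15 subjects × 2 = 30 nuclei, which covers 27; 15 × 1 does not. Two sides per person is therefore the natural reading beside the figure of 15, but it is an inference.

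**3. Effect on the error rate.** The between-side correlation of the treatment difference, r, is not given, so a range is assumed. For 13 people with two sides and one with one side (27 differences), the effective number is 27² / (27 + 26r). The error rate comes from 400,000 simulated null data sets per value of r, using an ordinary two-sided t-test on the 27 differences at nominal 0.001:

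| r | Effective units | True two-sided error |
|---|---|---|
| 0 | 27 | 0.001 |
| 0.3 | 21 | 0.003 |
| 0.5 | 18 | 0.006 |
| 0.8 | 15 | 0.014 |
| 1.0 | 14 | 0.022 |

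With 15 or 30 people and two sides each, simulated for r up to 0.8, the results are nearly the same (0.015 at r = 0.8). More people do not cure the problem.

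**4. Size in subjects.** With two sides per person the design effect is 1 + r, which gives nuclei; dividing by 2 gives subjects: units × (1 + r) / 2, rounded up.

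| r | From the stated 27 | From the recomputed 39 |
|---|---|---|
| 0 | 13.5 → 14 | 19.5 → 20 |
| 0.3 | 17.6 → 18 | 25.4 → 26 |
| 0.5 | 20.3 → 21 | 29.3 → 30 |
| 0.8 | 24.3 → 25 | 35.1 → 36 |
| 1.0 | 27 | 39 |

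The cap of 30 is reached when 39(1 + r)/2 = 30, that is r = 60/39 − 1 = 0.54.

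**5. Check on the approximation.** Averaging the two sides makes the standardised effect 0.714/√((1 + r)/2). A t-test on one value per subject then needs 23, 28, 31, 36 and 39 subjects at the five correlations. Fewer degrees of freedom add up to three subjects at low r. The conclusion that the cap is reached near r = 0.5 is unchanged.

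**The case against.** The strongest reply is that section 3.2.6 only sizes the study. Section 3.2.10 specifies no side-level test, and its statement that patients serve as their own controls could be taken to point to the patient as the unit. This stands in part. A reader might infer that the plan's analysis has invalid standard errors and that alpha is certainly exceeded. The documents do not support that, because the final analysis is not specified.

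Second, the correlation is unknown. Section 2 concerns the level of the resting beta rhythm, not the difference between adaptive and continuous stimulation, and it says nothing about Vrms, which drives the size. At zero correlation alpha is held. This stands, and it is why a range is shown from 0.

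Third, with up to 30 people, 27 nuclei could be one per person. Bilateral symptoms are required, but no section states that both sides are analysed. A reader might also infer that UPDRS III will be entered once per nucleus, which corresponds to correlation 1.0; nothing in the documents says so. Both points stand as limits.

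None of this removes the need for a change. The sizing paragraph is the only guide to the test, it counts nuclei, and no rule for two sides exists. Nor can one answer that any correction fits within 30 subjects: that holds only from the unreproduced 27. Pilot status lowers the stakes, but the plan itself claims significance at a stated alpha.

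**Conclusion.** The concern holds conditionally. The size is counted in nuclei without allowance for two sides in one person, and no unit of analysis is named. If both sides are analysed as independent, and their differences are correlated at 0.3 to 0.8, the nominal 0.001 becomes about 0.003 to 0.014; the limits are 0.001 at correlation 0 and 0.022 at 1.0. Use of both sides and a positive correlation are assumptions: plausible, but not documented.

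What does not depend on those assumptions is that 27 does not follow from the stated inputs. A two-sided test needs 39 independent units, and 27 give about 52% power. With two sides per person, the cap of 30 gives the stated 80% power only up to a correlation of about 0.5.

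These sizes use the plan's effects for stimulation on versus off. The study's question is adaptive versus continuous stimulation, for which the documents give no mean and SD, so they correct the arithmetic rather than establish the size that comparison needs.

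**What to change.** - **Unit of analysis.** State in section 3.2.10 that UPDRS III, stepping, gait and speech are analysed with one value per subject and condition.
- **Side-level outcomes.** For beta power, Vrms and tremor, use a mixed model with a random subject effect, set up so that it allows the treatment difference to be correlated between sides, or average the two sides within each subject first. State whether both sides are used.
- **Sample size.** Restate it in subjects as independent units × (1 + correlation) / 2, over a stated range of correlations. State sidedness and start from the corrected base (39 if two-sided), or explain how 27 was obtained.
- **Power and alpha.** Where the range exceeds 30 subjects, restate the power or alpha that the study can deliver rather than enrol more patients.

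The cost is revised protocol and SAP wording, with no change to visits or procedures. The downside is that the stated size or power becomes less favourable.
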